APPENDIX VI – PROHIBITED MEDICATIONS

Drug class	Agent	Wash-out (period of time that the medication should be discontinued prior to administration of the first dose of protocol treatment)*
Inducers of CYP3A4		
Antibiotics	All rifamycin class agents (rifampicin, rifabutin, rifapentine)	14 days
Anticonvulsants	Phenytoin, carbamazepine, barbiturates (phenobarbital)	14 days
Antiretrovirals	Efavirenz, nevirapine, tipranavir, etravirine	14 days
Glucocorticoids (oral) (pre-medication before the administration of taxanes is allowed)	Chronic use of cortisone (> 50mg), hydrocortisone (> 40 mg), prednisone or prednisolone (> 10 mg), methylprednisolone or triamcinolone (> 8 mg), betamethasone or dexamethasone (> 1.5 mg). Glucocorticoid daily doses (oral) ≤ 1.5 mg dexamethasone (or equivalent) are allowed. Short term steroid use (up to 2 weeks) is allowed. Premedication for taxane treatment is permitted.	14 days
Other	St. John's Wort, modafinil	14 days
Inhibitors of CYP3A4		
Antibiotic	clarithromycin, erythromycin, troleandomycin, flucloxacillin	7 days
Antifungals	itraconazole, ketoconazole, fluconazole (> 150 mg daily), voriconazole	7 days
Antiretrovirals, Protease Inhibitors	delaviridine, nelfinavir, amprenavir, ritonavir, indinavir, saquinavir, lopinavir, atazanavir	7 days
Calcium channel blockers	verapamil, diltiazem	7 days
Antidepressants	nefazodone, fluvoxamine	7 days
GI Agents	Cimetidine**, aprepitant	7 days
Other	Grapefruit, grapefruit juice, star fruit, papaw amiodarone	7 days 6 months
Substrates of CYP2C8, Pgp, BCRP and OATP1B1		
Antidiabetics	Repaglinide	1 day
Statins	Rosuvastatine	1 week
Cardiac glycosides	Digoxin, digitoxin	2 weeks
Miscellaneous		
Antacids	Magnesium and aluminium hydroxide, simethicone, calcium carbonate, magnesium carbonate	1 hour before and after dosing
Herbal or dietary supplements and traditional Chinese medicines	Ginkgo biloba, kava, grape seed, valerian, ginseng, Echinacea , evening primrose oil.	14 days

* All patients must have observed the specified washout period for all prohibited drugs prior to inclusion.

** Note: cimetidine may be used as taxane pre-medication if this is the local institutional practice

Active substance by interaction	Interaction – Change in everolimus AUC/C _{max} Geometric mean ratio (observed range)	Recommendations concerning co-administration
Potent CYP3A4/PgP inhibitors		
Ketoconazole	AUC ↑ 15.3-fold (Range 11.2-22.5) C _{max} ↑ 4.1-fold (Range 2.6-7.0)	Concomitant treatment of everolimus and potent inhibitors is not recommended.
Itraconazole, posaconazole, voriconazole	Not studied. Large increase in everolimus concentration is expected.	
Telithromycin, clarithromycin		
Nefazodone		
Ritonavir, atazanavir, saquinavir, darunavir, indinavir, nelfinavir		
Moderate CYP3A4/PgP inhibitors		
Erythromycin	AUC ↑ 4.4-fold (Range 2.0-12.6) C _{max} ↑ 2.0-fold (Range 0.9-3.5)	Use caution when co-administration of moderate CYP3A4 inhibitors or PgP inhibitors cannot be avoided. If patients require co-administration of a moderate CYP3A4 or PgP inhibitor, dose reduction to 5 mg daily or 5 mg every other day may be considered. However, there are no clinical data with this dose adjustment. Due to between subject variability the recommended dose adjustments may not be optimal in all individuals, therefore close monitoring of side effects is recommended.
Verapamil	AUC ↑ 3.5-fold (Range 2.2-6.3) C _{max} ↑ 2.3-fold (Range 1.3-3.8)	
Ciclosporin oral	AUC ↑ 2.7-fold (Range 1.5-4.7) C _{max} ↑ 1.8-fold (Range 1.3-2.6)	
Fluconazole	Not studied. Increased exposure expected.	
Diltiazem		
Amprenavir, fosamprenavir	Not studied. Increased exposure expected.	
Grapefruit juice or other food affecting CYP3A4/PgP	Not studied. Increased exposure expected (the effect varies widely).	Combination should be avoided.
Potent CYP3A4 inducers		
Rifampicin	AUC ↓ 63% (range 0-80%) C _{max} ↓ 58% (range 10-70%)	Avoid the use of concomitant potent CYP3A4 inducers. If patients require co-administration of a potent CYP3A4 inducer, an everolimus dose increase from 10 mg daily up to 20 mg daily should be considered using 5 mg increments applied on Day 4 and 8 following start of the inducer. This dose of everolimus is predicted to adjust the AUC to the range observed without inducers. However, there are no clinical data with this dose adjustment. If treatment with the inducer is discontinued, the everolimus dose should be returned to the dose used prior to initiation of the co-administration.
Corticosteroids (e.g. dexamethasone, prednisone, prednisolone)	Not studied. Decreased exposure expected.	
Carbamazepine, phenobarbital, phenytoin	Not studied. Decreased exposure expected.	
Efavirenz, nevirapine	Not studied. Decreased exposure expected.	
St John's Wort (Hypericum perforatum)	Not studied. Large decrease in exposure expected.	Preparations containing St John's Wort should not be used during treatment with everolimus

[figure not shown]

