3.3.4 Clinical Safety of Ribociclib As Single Agent

As of 15-Jun-2015, 157 patients have been treated with single agent ribociclib in the first-in-human (FIH) phase I study; 85 patients have been treated in the initial dose escalation part for the 3 week on/1 week off regimen and 47 patients in the dose expansion part of the study; 18 patients were enrolled for the continuous dosing regimen with ribociclib and, 7 patients were enrolled in the liquid formulation cohort.

Patients with advanced solid tumors or lymphomas were treated with increasing doses of ribociclib orally, once daily (qd) for 21 days followed by a 1-week rest (28-day cycle). Doses ranging from 50 mg to 1200 mg were

evaluated on this schedule. Treatment has been discontinued in 120 (90%) patients; the primary reasons for treatment discontinuation were: disease progression (106 [80%] patients); adverse events (AEs) (7 [5%] patients); death (2 [1.5%] patients); withdrawal of consent (3 [2%] patient); and loss to follow up (1 [1%] patient).

The most frequently reported AEs ($\geq 10\%$), regardless of grade, causality and ribociclib dose were: nausea (52.3%); fatigue (40.9%); diarrhea (37.1%); vomiting (35.6%); neutropenia (34.1%); anemia (32.6%); decreased appetite, thrombocytopenia (23.5% each); white blood cell count decrease (22.7%); leukopenia (22%); constipation (21.2%); dyspnea (20.5%); asthenia (19.7%); cough (18.2%); hyperglycemia (17.4%); headache, hypoalbuminemia (16.7% each); ECG QT prolonged (15.9%); abdominal pain, back pain, lymphocyte count decrease, pyrexia (15.2% each); AST increase, blood creatinine increased, dizziness, lymphopenia (14.4% each); peripheral edema (13.6%); neutrophil count decreased (12.9%); ALT increase, pain in extremity (12.1% each) and hypocalcemia (11.4%).

For either continuous or intermittent dosing, the onset of neutropenia (most frequently Grade 2) occurs by Day 15, reaching a nadir in the third or fourth week with recovery during the week of drug holiday for the three weeks on/one week off schedule. Some patients require additional time for recovery (7 to 14 days). QT changes become evident in the first cycle by Day 8 and later (once steady state is reached), are associated with the maximum drug levels between 1 to 8 h post-dose, and remain stable or improve in subsequent cycles.

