As of 15-Jun-2015, asymptomatic Grade 2 QTcF prolongation was observed with increasing frequency when increasing the dose starting at 600 mg: ten patients (13.5%) in the 600 mg cohort, three patients (21%) in the 750 mg cohort, four patients (31%) in the 900 mg cohort, and two patients (67%) in the 1200 mg cohort. Four patients (5.4%) at 600 mg and two patients (15%) at 900 mg had asymptomatic QTcF prolongation that resulted in a QTcF interval of 500 ms or more. As compared to baseline value, QTcF prolongation was at least 30 msec in 2 patients (50%) at 250mg, 2 (40%) at 350 mg and 400 mg, 59 (79.7%) at 600 mg, 11 (78.6%) at 750 mg, 11 (85%) at 900 mg and 2 (67%) at 1200 mg; and at least 60 msec in 23%, 0%, 39% and 67% of patients at 600 mg, 750 mg, 900 mg and 1200 mg, respectively. One grade 1 atrioventricular block of first degree was reported as related to ribociclib given at the dose of 140 mg. One grade 1 atrioventricular block of first degree was reported as related to ribociclib given at the dose of 140 mg. No other cardiac abnormalities were observed as related adverse events in any patient.

There have been no deaths related to study drug reported on study [CLEE011X2101]. The following serious adverse events shown in TABLE 1-1 have been reported with a suspected causal relationship in study [CLEE011X2101] as of 6-Aug-2015. For a complete list of AEs, all grades and Grade 3/4 that are suspected to be related to ribociclib refer to the ribociclib Investigators Brochure.

Serious suspected adverse events which have occurred with ribociclib (single agent)	
System Organ Class Preferred Term	Preferred Term
Blood and lymphatic system disorders	Anaemia, Febrile neutropenia, Neutropenia, Thrombocytopenia
Gastrointestinal disorders	Diarrhoea, Nausea, Pancreatitis
General disorders and administration site conditions	Generalized oedema
Infections and infestations	Herpes simplex
Investigations	Blood creatinine increased, Electrocardiogram QT prolonged

Events in *italic font* indicate those events which are newly included since the previous edition of the reference safety information.

Refer to ribociclib Investigators Brochure for more details.

Table 6: Serious adverse events with a suspected causal relationship with ribociclib single agent

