Physicians should always manage patients according to their medical judgment based on the particular clinical circumstances.

Table 21: Ribociclib dose adjustment and management recommendations for hematological adverse reactions

Additional follow up for QTc prolongation

For All Grades

- Check the quality of the ECG and the QT value and repeat if it needed
- Perform analysis of serum electrolytes (K⁺, Ca⁺⁺, Phos, Mg⁺⁺). If outside of the normal range, interrupt ribociclib administration, correct with supplements or appropriate therapy as soon as possible, and repeat electrolytes until documented as normal.
- Review concomitant medication usage for the potential to inhibit CYP3A4 and/or to prolong the QT interval.
- Check compliance with correct dose and administration of ribociclib.
- Consider collecting a time matched PK sample; record date and time of last study drug intake

1*

QTc 450-480 ms

No change

2*

QTc 481-500 ms

Interrupt ribociclib.

Perform a repeat ECG within one hour of the first QTcF of ≥ 481 ms.

If QTcF < 481 ms, restart ribociclib at the same dose. No dose adjustment required for first occurrence.

If QTcF remains ≥ 481 ms, repeat ECG as clinically indicated until the QTcF returns to < 481 ms. restart ribociclib at the same dose. No dose adjustment required for first occurrence.

If QTcF ≥ 481 ms recurs, ribociclib should be reduced by 1 dose level.

Repeat ECGs 7 days and 14 days after dose resumption (then as clinically indicated) for any patients who had therapy interrupted due to QTcF ≥ 481 ms

3

QTc ≥ 501 ms on at least two separate ECGs

Interrupt ribociclib. Transmit ECG immediately and confirm prolongation/abnormalities.

Perform a repeat ECG within one hour of the first QTcF of ≥ 501 ms.

If QTcF remains ≥ 501 ms, consult with a cardiologist (or qualified specialist) and repeat cardiac monitoring as indicated until the QTcF returns to < 481 ms.

If QTcF returns to < 481 ms, ribociclib will be reduced by 1 dose level.

Repeat ECGs 7 days and 14 days after dose resumption (then as clinically indicated) for any patients who had therapy interrupted due to QTcF ≥ 501 ms

If QTcF of ≥ 501 ms recurs, discontinue ribociclib.

4* [QT/QTc ≥ 501 or > 60 ms change from baseline] and [Torsades de pointes or polymorphic ventricular tachycardia, or signs/symptoms of serious arrhythmia]

Discontinue ribociclib.

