8.5.4 Prohibited concomitant therapy

Use of the following treatments is NOT allowed during the study:

- Investigational or commercial anticancer agents, such as chemotherapy, immunotherapy, targeted therapy, biological response modifiers, or endocrine therapy other than the once listed must not be given to patients.
- Hormone replacement therapy, topical estrogens (including any intra-vaginal preparations), Megestrol acetate and selective estrogen-receptor modulators (e.g. Raloxifene) are prohibited.
- Patients receiving concomitant immunosuppressive agents or chronic corticosteroids use, after taking the first dose of study drug in cases outlined below: Topical applications (e.g. rash), inhaled sprays (e.g. obstructive airways diseases), eye drops or local injections (e.g. intra-articular) are allowed. Long term low dose therapy, i.e. ≤ 10 mg/d prednisolone equivalent is permissible.
- Hematopoietic growth factors (e.g. Erythropoietins, G-CSF and GM-CSF) are not to be administered prophylactically. Use of these must be reserved to cases of Grade 3 or 4 neutropenia and anemia as per the labeling of these agents.
- Where possible, it is recommended to avoid drugs or substances known to be inhibitors or inducers of the isoenzyme CYP3A:
 - Co-administration with strong CYP3A inhibitors (e.g. Ketoconazole, Itraconazole, Ritonavir), and strong inducers (e.g. Rifampin, Rifabutin) should be avoided.
 - Co-administration with moderate CYP3A inhibitors (e.g. erythromycin, fluconazole, calcium channel blockers, benzodiazepines) and moderate inducers (e.g., carbamazepine, phenobarbital, phenytoin) should also be avoided if possible or otherwise subject to caution (e.g. increased frequency of safety monitoring).
 - Inhibitors – prohibited 7 days before dosing (6 months for amiodarone) and during protocol treatment
 - Inducers – prohibited 14 days before dosing and during protocol treatment

Sevilla orange, grapefruit and grapefruit juice affect cytochrome P450 and P-gp activity and must therefore be avoided during study drug intake.

Because the composition, pharmacokinetics and metabolism of many herbal supplements are unknown, concurrent use of all herbal supplements is prohibited during protocol treatment.

APPENDIX VI – PROHIBITED MEDICATIONS lists clinically relevant CYP3A inhibitors, inducers and the definition of strong and moderate inhibitors/inducers.

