Tumor evaluation according to RECIST guidelines (version 1.1) ¹² (see protocol section 10.2.1.)		X ¹⁵	X ¹¹		
Tumor markers ¹⁸		X	X		
12-lead ECG		X ¹⁰	X ²⁰	X ²⁰	
Quality of life (EORTC QLQ-C30 and -BR23)		X ¹³	X	X	
Review of inclusion and exclusion criteria		X			
Dispense of everolimus/ribociclib		X			
Additional supply of everolimus/ribociclib if necessary			X		
Tablet count (everolimus/ribociclib cohort only)			X	X	
Collection of unused everolimus				X	
Reminding the patient of the follow-up procedures planned				X	
Survival			X	X	X

¹ Cf. section 16.4

² Patient may participate in the study if this consent was not granted. However, in this case body material must not be sampled for the purpose of translational medical investigations

³ Cf. section 11.1

⁴ Estrogen and progesterone status each graded positive or negative

⁵ Results must be obtained prior inclusion visit. Blood sampling for CTC count and assessment of their HER2 status should be scheduled at least one week after last application of investigational agents of any type or anticancer therapy.

⁶ If applicable: additional blood sampling in patients who consent to participate in translational research (part of patient information and consent form – part 1). If a patient objects to blood sampling for this purpose, she may nevertheless participate in the study.

⁷ Must include: hemoglobin, hematocrit, red blood cell count, differential white blood cell count, platelet count

⁸ Must include: total and direct bilirubin, ALT, AST, albumin, serum creatinine, BUN or urea, potassium, magnesium, fasting glucose, fasting triglycerides and fasting serum cholesterol. Ribociclib-cohort: sodium, potassium, calcium, phosphorous. GGT, AP, and LDH; at baseline and if clinically indicated: total cholesterol, LDL-cholesterol, HDL-cholesterol and triglycerides. Monitor electrolytes at the beginning of each cycle for 6 cycles. and as clinically indicated.

⁹ Results obtained within the preceding 7 days may be employed

¹⁰ Results obtained within the 3 preceding weeks may be employed

¹¹ The therapy response evaluation should be performed every 3 months or if medically indicated. Treatment response evaluation should be performed together with the determination of CTCs

¹² The same method should be used on every assessment

¹³ Results obtained within the preceding week may be employed

¹⁴ Only if medically indicated

- ¹⁵ Results obtained within the 6 preceding week may be employed

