- ¹⁶ Documentation of end of protocol treatment and documentation of planned therapy after end of protocol treatment
- ¹⁷ CTC count with Analysis Kit should be performed every 3 months (not in the eribulin cohort). Generally treatment response evaluation should be performed together with the determination of CTCs as part of clinical trial. CTC count at conclusion visit (i.e. end of treatment or progress) should be performed for both cohorts with Analysis Kit.
- ¹⁸ Tumor markers are assessed on each tumor evaluation: CA15-3 is mandatory, CA125 and CEA are optional
- ¹⁹ Blood sampling with Analysis Kit as part of translational research projects (only with informed consent part 3) at week 3 - 4 and at week 9 – 12 (in the eribulin cohort CTC count should be performed after cycle 1 and 3, in the everolimus/ribociclib cohort CTC count should be performed in the mentioned period).
- ²⁰ Ribociclib-cohort:
ECG: Cycle 1 d14, and at the beginning of the second cycle, and as clinically indicated.
Liver Function Test (LFT): monitor LFTs every 2 weeks for the first 2 cycles, at the beginning of each subsequent 4 cycles, and as clinically indicated.
- ²¹ Eribulin-cohort: monitoring of complete blood counts should be performed on all patients prior to each dose of eribulin.

*Data must be obtained before screening

**Patients may be screened without obtaining this additional information. Documentation of these data will be reimbursed additionally.

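### The single, mainly CYP3A-based prohibited-medication list has no QT rule for ribociclib and omits three drugs the protocol advises against with eribulin

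*Protocol*

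**What the plan says.** Section 8.5.4 lists treatments not allowed during the study and has no split by cohort. Its interaction rule concerns CYP3A. Inhibitors are "prohibited 7 days before dosing (6 months for amiodarone) and during protocol treatment", and Appendix VI is described as a document that "lists clinically relevant CYP3A inhibitors, inducers and the definition of strong and moderate inhibitors/inducers". The Appendix VI washout table carries the footnote "All patients must have observed the specified washout period for all prohibited drugs prior to inclusion".

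On ribociclib, section 3.3.4 reports that "asymptomatic Grade 2 QTcF prolongation was observed with increasing frequency when increasing the dose starting at 600 mg" and dates QT changes to Day 8 of the first cycle onwards. Table 19 sets 600 mg/d as the starting dose. QT-prolonging co-medication is mentioned for ribociclib only in the QTc follow-up instructions of section 8.3.2.1: "Review concomitant medication usage for the potential to inhibit CYP3A4 and/or to prolong the QT interval".

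On eribulin, section 3.4.5 advises against hepatic transporter inhibitors and names examples. Section 3.4.6 recommends ECG monitoring when eribulin is started in patients taking QT-prolonging drugs.

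Section 8.5.3 permits supportive drugs subject to an exception that points to section 8.4.3. That section describes the undesirable effects of eribulin.

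**The concern.** A site deciding whether a patient may take or start a drug will look in 8.5.4 and Appendix VI. These should hold the restrictions that follow from each study drug's known risks. As written, a ribociclib patient may enter on, or be given during treatment, another QT-prolonging drug without breaking any rule, unless the drug happens to be listed for a CYP3A reason (amiodarone is an example). An eribulin patient may likewise take a drug that the protocol's own pharmacology section advises against.

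The main stake is patient safety. There is also a cost in interpretation: QTc values drive ribociclib interruptions and dose reductions under 8.3.2.1, and a QTc event in a patient on a second QT-prolonging drug cannot be cleanly attributed.

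**Working it through.** There is no sample-size or error-rate figure to reproduce. The check sets the sections side by side.

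**1. Can 8.5.4 hold drug-specific rules?** Yes. It already has one for everolimus (live vaccines). It has none specific to ribociclib or eribulin.

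**2. QT-based restrictions in the operative list.** Section 8.5.4 covers anticancer agents, hormonal agents, immunosuppressants and corticosteroids, growth factors, CYP3A inhibitors and inducers, citrus products, herbal supplements and live vaccines. The Appendix VI washout table covers CYP3A4 inducers, CYP3A4 inhibitors, substrates of CYP2C8, Pgp, BCRP and OATP1B1, antacids and herbals. The second Appendix VI table concerns everolimus exposure only. Entries made on QT grounds: 0.

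**3. Size of the QT signal at the study dose (3.3.4, single-agent phase I).**
- Grade 2 QTcF prolongation: 10 patients, 13.5%.
- QTcF of 500 ms or more: 4 patients, 5.4%.
- Increase of at least 60 ms: 23%.
- The first two agree on the denominator: 10 / 0.135 ≈ 74 and 4 / 0.054 ≈ 74.

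These are rates for ribociclib itself. The protocol gives none for ribociclib plus another QT-prolonging drug.

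**4. What each ribociclib safeguard does.**
- Entry limits (section 5.1): QTcF below 450 ms, heart rate 50–90 bpm, normal sodium, potassium and calcium. They select on the ECG and laboratory values, not on co-medication. For the entry ECG, Appendix II allows: "Results obtained within the 3 preceding weeks may be employed".
- Control Visits (synopsis and section 9.1): ECG and co-medication recording at each visit, every 2–4 weeks. Appendix II footnote 20 gives fixed times: "ECG: Cycle 1 d14, and at the beginning of the second cycle, and as clinically indicated". These detect prolongation and record the drug.
- QTc follow-up (8.3.2.1): co-medication review at any grade, starting at 450 ms. It acts after prolongation is seen.
- Section 8.5.1: patients consult before taking new drugs. The investigator then has no QT rule to apply.

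None of these bars the exposure.

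**5. Eribulin transporter inhibitors.** Section 3.4.5 names 11 single agents.
- In the washout table: ritonavir, saquinavir, lopinavir, verapamil, clarithromycin, and efavirenz (as an inducer) = 6.
- Reached indirectly: cyclosporine = 1. It is in the everolimus table and falls under immunosuppressive agents in 8.5.4.
- Absent: quinine, quinidine, disopyramide, emtricitabine = 4.
- Check: 6 + 1 + 4 = 11.

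Setting emtricitabine aside, on the assumption that it would be used only for HIV infection, which is an exclusion when known, leaves 4 − 1 = 3.

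**6. Eribulin ECGs.** Section 3.4.6 describes a 26-patient study with QT prolongation on Day 8 and none on Day 1. The eribulin cohort has an ECG at inclusion and at the Conclusion Visit. The Control Visit ECG in the synopsis, section 9.1 and footnote 20 is for ribociclib only.

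**The case against.** The strongest reply is that ribociclib patients are well monitored. ECG and co-medication are assessed together at each Control Visit, and because entry requires QTcF below 450 ms, any later value at or above that limit prompts a review for QT-prolonging drugs. Electrolytes are checked at the start of each of the first 6 cycles. This stands, and it limits the size of the point, but it describes detection.

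For eribulin, severe congenital long QT is an exclusion and potassium and magnesium are measured at baseline and at each Control Visit. Section 3.4.5 also says only that transporter inhibitors are not recommended, in an open-ended list, and a drug so described need not be prohibited. That is fair, so the right strength is avoidance. Section 8.5.4 already holds entries of that strength for CYP3A drugs.

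A reader might infer three stronger claims, which the protocol does not support.
- That patients go 34 days without an ECG. An entry ECG 21 days before recruitment plus 13 days from Day 1 to Day 14 does give 34, but 21 of those days precede any ribociclib, only 6 follow Day 8, and a co-medication rule would not change the ECG schedule.
- That the ketoconazole washout should be lifted for eribulin because 3.4.5 reports exposure unaffected by it. Appendix VI also classes ketoconazole as a PgP inhibitor, and 3.4.5 advises against Pgp inhibitors, so keeping it is a defensible choice.
- That the protocol contradicts itself on QT. It does not; the rule is simply missing.

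The 8.5.3 cross-reference is a numbering slip, since 8.5.4 applies in its own right.

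**Conclusion.** The point holds as a cheap improvement. The shared list does not carry over two risks that the protocol describes: QT-prolonging co-medication with ribociclib (no restriction in 8.5.4 or the visible Appendix VI) and, for eribulin, three named transporter inhibitors together with the conditional ECG monitoring of 3.4.6. Existing safeguards reduce the consequence for ribociclib but do not prevent the exposure.

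The conclusion rests on the text available. One item at the end of Appendix VI is not reproduced, so a QT entry there cannot be wholly excluded, although 8.5.4 describes the appendix as a CYP3A list. The investigator's brochure and the patient information sheets were not seen. The protocol does not say how often such co-medication is used, so no number of affected patients is claimed.

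**What to change.** In 8.5.4 and Appendix VI, add entries marked by study drug:
- **Ribociclib:** avoid QT-prolonging drugs, naming Class Ia and Class III antiarrhythmics, and check co-medication for them before the first dose.
- **Eribulin:** avoid the hepatic transporter inhibitors of 3.4.5, naming quinine, quinidine and disopyramide, and perform the ECG monitoring of 3.4.6 when a QT-prolonging drug is used.

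In 8.5.3, change the reference from 8.4.3 to 8.5.4. Leave the existing washout entries, ketoconazole included, and the ribociclib ECG times as they are.

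The cost is a few lines of text, an edit to one appendix table and one corrected cross-reference. Sample size and analysis are unaffected. A few patients may need a change of co-medication, and eribulin patients on a QT-prolonging drug would have additional ECGs.
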